## **Study Protocol**

The objective of this research is to develop and test an automatically-adjusting prosthetic socket system for prosthesis users. The system integrates with a range of adjustable socket technologies, including those that are commercially available. The system we will develop allows small size adjustments for both tightening and loosening the socket. Adjustable panels may be attached to the prosthetic liner using a mechanical method such as Velcro, adhesive, or a thin strap or clasp to allow the liner to be pulled out with the panels when the socket is loosened. The user does not need to remove the prosthesis or bend down to make adjustments. The system will later be enhanced to automatically change the fit of an adjustable socket without distracting the user. It helps to maintain consistent limb fluid volume when the service member or Veteran is actively using the prosthesis. It does this using information from sensors within the socket and small motors that control adjustable panels in the socket wall.

The developed technology will apply two concepts learned from our recent research funded by the DOD. One concept is to slowly enlarge the socket the right amount during dynamic activity. The other concept is to loosen the socket during resting to allow healthy fluid return to the limb.

A multi-aim, longitudinal study will be carried out to test this new prosthetic technology. All aims of the study will involve similar procedures meant to investigate the use of our adjustable socket (the interface between the prosthesis and residual limb), with iterative improvements made in each aim.

### **SPECIFIC AIMS:**

Aim 2: Assess the performance of an adjustable socket in our laboratory.

Aim 3: Assess how prosthetic users use a wireless, adjustable socket to manage change in limb volume.

Aim 4: Assess the performance of an automatic, adjustable socket in our laboratory.

Aim 6A: Assess the performance of an adjustable socket in our laboratory that is able to quickly enlarge and quickly return to normal size to enable full or partial doffing while seated.

Aim 6B: Assess how prosthetic users respond to an adjustable socket that is able to quickly enlarge and quickly return to normal size automatically to enable full or partial doffing while seated.

Aim 8: Assess how prosthetic users respond to an adjustable socket, which is attached to their liner, that is able to enlarge while seated and return to normal size before ambulation.

Aim 9: Assess how prosthetic users respond to an adjustable socket, which is attached to their liner, that is able to quickly enlarge and quickly return to normal size automatically during ambulation.

Aim 10: Involves in-field testing of the adjustable prosthetic system developed in the prior aims. Subjects will use the test socket in 3 different configurations throughout the course of this study: (A) automatic control mode, (B) manual control mode, and (C) adjustment disabled mode. (A) In the automatic control mode, sensors that are built into the socket will be used to monitor the movement and position of the limb within the socket and use this information to automatically adjust the socket panels in an effort to improve the fit. Adjustments may occur while they are sitting, standing, and walking. The system will be integrated into an app on a smartphone. We will provide the phone. (B) In the manual control mode subjects will be able to make adjustments to the panels using the smartphone app. Changes will not be made automatically. (C) In the disabled mode, the ability to adjust panels will be turned off.

A description of the study procedures that will be used is given here; the attached table outlines what specific procedures will be done at the study visits for each aim:

|  | Aim 2, Aim 8,
Aim 9   | Aim 3  | Aim 4  | Aim 6A  | Aim 6B   |
|--|--|--|--|---|--|
| Visit 1—may not be needed if the participant has already had a socket made and has answered health questions | 3 hours
-Walk on treadmill
-Questions related to prosthesis and limb health
-Scan socket to make an adjustable test socket
-vascular tests   | 3 hours
-Walk on treadmill
-Questions related to prosthesis and limb health
-Scan socket to make an adjustable test socket
-vascular tests   | 3 hours
-Walk on treadmill
-Questions related to prosthesis and limb health
-Scan socket to make an adjustable test socket
-vascular tests   | 2 hours
-Questions related to prosthesis and limb health
-Scan socket to make an adjustable test socket
-vascular tests  | 2 hours
-Questions related to prosthesis and limb health
-Scan socket to make an adjustable test socket
-vascular tests   |
| Visit 2—approximately 4 weeks after visit 1, when their adjustable test socket is ready                      | 3 hours
-May place electrodes on skin of residual limb
-Test socket fit
-May place sensors onto socket and/or liner to measure activity and limb movements in the socket.
-Stand then walk on treadmill at varying speeds while adjustable socket is controlled by researchers to reduce limb movement within the socket | 5 hours
-May place electrodes on skin of residual limb
-Test socket fit
-May place sensors onto socket and/or liner to measure activity and limb movements in the socket
-May wear heart rate monitoring watch
-Teach participant how to use the controller to adjust the socket, practice in the lab and then around the building; once comfortable leave the lab for up to 4 hours wearing the socket and conduct normal activities or follow a more structured protocol. | 3 hours
-May place electrodes on skin of residual limb
-Test socket fit
-May place sensors onto socket and/or liner to measure activity and limb movements in the socket.
-May wear heart rate monitoring watch
-Stand then walk on treadmill at varying speeds while adjustable socket is controlled automatically to reduce limb movement within the socket | 4 hours
-May place electrodes on skin of residual limb
-Test socket fit
-May place sensors onto socket and/or liner to measure activity and limb movements in the socket.
-Perform series of sit-to-stand and stand-to-sit transitions, with periods of walking or resting in between.
Researchers will make the socket release to become larger when seated and recover back to normal size when preparing to stand | 7 hours
-May place electrodes on skin of residual limb
-Test socket fit
-May place sensors onto socket and/or liner to measure activity and limb movements in the socket.
-Teach participant how to use the adjustable socket with release mechanism; they will practice in the lab and around the building while being monitored by a staff member. Once comfortable they will leave the lab for 3-4 hours wearing the socket and conduct normal activities |

|  | Aim 10   |
|--|--|
| Lab Visit 1—may not be needed if the participant has already had a socket made and has answered health questions | Up to 2 hours
-Walk on treadmill
-Questions related to prosthesis and limb health
-Scan socket to make an adjustable test socket
-vascular tests   |
| Lab Visit 2—up to 3 weeks after visit 1, when their adjustable test socket is ready                              | 3 hours
-Test socket fit
-May place sensors onto socket and/or liner to measure activity and limb movements in the socket
-Teach participant how to use the adjustable socket in the 3 different modes that will be tested. Once they are comfortable, they will leave the lab for 4-7 days with socket in the first mode to be tested. |
| Research engineer visits (2) –at the end of each of the first two socket test modes                              | 1-2 hours each.
-Questionnaire and dialog regarding socket test mode that was just completed
-Socket will be changed over to next test mode
-Refresh participant training on how to use the new test mode
-Once comfortable in new test mode, subject will continue using the mode for next 4-7 days.                                |
| Lab Visit 3—at the end of the 3 rd socket test mode   | 1-3 hours
-Questionnaire and dialog regarding socket test mode that was just completed AND all socket modes tested in the study
-Original socket will be returned to initial state and all study instruments will be retained by the lab   |

Primary quantitative data will be collected via custom study instruments, such as a bioimpedance measurement system to assess limb volume changes and inductive sensors built into the test socket wall to measure limb movement/distance. Qualitative data will be collected from participants directly through self-report of their health history, during study procedures. All data for this research will be collected prospectively.

**Statistical Analysis Plan:****Aim 2, Aim 6A, Aim 6B, and Aim 8**

The primary outcome measure of change in limb volume was taken at times of socket enlargement and socket reduction. A Shapiro-Wilk test will be used to determine normalcy. Normally distributed data will be compared using paired t-tests. If data is not normally distributed, a Wilcoxon Signed Rank Test will be used to make comparisons. A significance level of 0.05 will be used to determine whether measured differences in limb volume were statistically significant between interventions.

**Aim 3**

The primary outcome measure of change in limb movement was taken at times of socket enlargement and socket reduction. A Shapiro-Wilk test will be used to determine normalcy. Normally distributed data will be compared using paired t-tests. If data is not normally distributed, a Wilcoxon Signed Rank Test will be used to make comparisons. A significance level of 0.05 will be used to determine whether measured differences in limb movement were statistically significant between socket enlargement and socket reduction.

**Aim 4**

The primary outcome, integral of absolute error, was measured as participants walked with the adjustable socket's controller maintaining a set socket volume (set point). A Shapiro-Wilk test will be used to determine normalcy. Normally distributed data will be compared using paired t-tests. If data is not normally distributed, a Wilcoxon Signed Rank Test will be used to make comparisons. A significance level of 0.05 will be used to determine whether differences were statistically significant between interventions.

**Aim 9**

The primary outcome measure of participants who experienced increase in limb fluid volume was assessed after a structured protocol involving socket enlargements and socket reductions. A Shapiro-Wilk test will be used to determine normalcy. Normally distributed data will be compared using paired t-tests. If data is not normally distributed, a Wilcoxon Signed Rank Test will be used to make comparisons. A significance level of 0.05 will be used to determine whether differences were statistically significant between interventions.

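### Aim 9: the primary outcome is worded as a yes/no status per participant, but the SAP gives it paired tests for quantitative data and names no pair

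*Combined protocol and SAP*

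**What the plan says.** The Aim 9 section of the SAP states: "The primary outcome measure of participants who experienced increase in limb fluid volume was assessed after a structured protocol". The protocol in question contains both directions of adjustment; the outcome is "assessed after a structured protocol involving socket enlargements and socket reductions". The section then calls for Shapiro-Wilk, a paired t-test if the data look normal, a Wilcoxon signed-rank test if they do not, and a 0.05 level to decide "whether differences were statistically significant between interventions". It does not say which interventions, and it gives no threshold or time points for an increase.

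Two other SAP sections use the same tests with more definition:

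- **Aims 2, 6A, 6B and 8:** "The primary outcome measure of change in limb volume was taken at times of socket enlargement and socket reduction".
- **Aim 3:** the test is whether "measured differences in limb movement were statistically significant between socket enlargement and socket reduction".

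Elsewhere, the Specific Aims describe one device behaviour for Aim 9, a socket "able to quickly enlarge and quickly return to normal size automatically during ambulation". In the study procedures table, the Visit 2 column that Aim 9 shares with Aims 2 and 8 lists one walking task: "Stand then walk on treadmill at varying speeds while adjustable socket is controlled by researchers to reduce limb movement within the socket". For electrodes the same cell says only "May place electrodes on skin of residual limb". The paragraph after the procedure tables gives bioimpedance limb volume as an example of the primary quantitative data.

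**The concern.** There are two separate defects.

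1. **Scale.** The outcome as worded is binary and is summarised as k of n. The named tests are for paired quantitative differences. No method for a proportion is given.
2. **Pair.** A paired test needs two values per person. The Aim 9 section describes one assessment, made after a protocol in which enlargement and reduction are both components. They are not presented as the two arms of a comparison, and no baseline or second condition is named.

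The second defect remains even if the first is read generously. For a primary outcome, this leaves the scale, the contrast and the definition of an increase to be settled at analysis. A responder count and a mean change answer different questions, and they need not agree in the same participants.

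**Working it through.** The plan gives no sample size, effect size, SD or event count for Aim 9, so there is no figure of its own to reproduce. The finding rests on the text. The calculations below only show what the gaps could do. All n, distributions and data values are assumed.

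**Sections side by side**

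| SAP section | Outcome | Scale as worded | Pair |
|---|---|---|---|
| Aims 2, 6A, 6B, 8 | change in limb volume | continuous | enlargement and reduction times given; contrast stated only as between interventions |
| Aim 3 | change in limb movement | continuous | enlargement vs reduction, explicit |
| Aim 4 | integral of absolute error | continuous | not named |
| Aim 9 | participants with an increase | yes/no | not named |

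Among these primary outcomes, only Aim 9 combines a yes/no wording with an unnamed pair.

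**1. Shapiro-Wilk on the outcome as worded.** I applied the test to every mixed set of 0/1 values, n = 6 to 30. The largest p anywhere is 0.0040 (n = 6, three ones), so normality is always rejected and the step carries no information.

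**2. If a second condition did exist.** Paired 0/1 differences can only be -1, 0 or +1. Over every non-constant set of such differences:

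| n | largest Shapiro-Wilk p | sets with p > 0.05 |
|---|---|---|
| 6 | 0.212 | 6 of 25 |
| 7 | 0.144 | 7 of 33 |
| 8 | 0.093 | 5 of 42 |
| 9 | 0.055 | 2 of 52 |
| 10 | 0.036 | 0 |
| 12 | 0.020 | 0 |
| 20 | 0.0015 | 0 |

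No set passes at any n from 10 to 30. At n = 6 to 9 the rule could select a t-test on three-valued data.

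**3. Undefined threshold.** Let change, in SD units, be Normal(0.5, 1). The share counted as an increase above threshold t is 1 - Φ(t - 0.5).

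- t = 0: 0.691
- t = 0.25: 0.599
- t = 0.5: 0.500
- t = 1: 0.309

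**4. Undefined scale.** Two invented sets of 12 percent changes, with an increase taken as above zero:

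- **Set 1:** 0.2, 0.3, 0.4, 0.5, 0.6, 0.7, 0.8, 0.9, -0.1, -0.2, -0.3, -0.15. Mean = (4.4 - 0.75)/12 = 0.304. Shapiro-Wilk p = 0.447, so the t-test applies: p = 0.027.
- **Set 2:** 0.2, 0.3, 0.3, 0.4, 0.4, 0.5, 0.5, 0.6, -1.5, -1.8, -2.0, -2.2. Mean = (3.2 - 7.5)/12 = -0.358. Shapiro-Wilk p = 0.0018, so signed-rank applies: p = 0.834.

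Both sets have 8/12 responders, with a Clopper-Pearson 95% CI of 0.349 to 0.901.

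**5. Precision if the responder outcome is kept.** Clopper-Pearson 95% CI at 50% responders:

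| k/n | 95% CI | width |
|---|---|---|
| 3/6 | 0.118 to 0.882 | 0.764 |
| 4/8 | 0.157 to 0.843 | 0.686 |
| 5/10 | 0.187 to 0.813 | 0.626 |
| 6/12 | 0.211 to 0.789 | 0.578 |
| 10/20 | 0.272 to 0.728 | 0.456 |

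These widths are a property of any small proportion. They show the cost of keeping the responder outcome and are not evidence of the defect.

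**The case against.** **The sponsor may have meant the continuous change.** Bioimpedance limb volume is given as primary quantitative data, and the Aim 8 analysis applies the same tests to change in limb volume. On that reading the tests can be valid. This stands as a likely intention, but the Aim 9 section does not state that outcome, and the pair would still be unnamed.

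**Signed-rank is not absurd on binary pairs.** Once zero differences are dropped, all absolute values tie. The exact signed-rank test is then equivalent to the sign test, which is exact McNemar. From n = 10 to 30 the normality rule would always lead there. This is correct, but it needs two conditions per participant, and none are named.

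**The gap is not unique to Aim 9.** The Aim 4 section also refers to interventions without naming them. True; what sets Aim 9 apart is that the outcome wording fails as well.

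**The procedures table is weak evidence.** Its shared column describes researcher control, while the Specific Aims describe automatic adjustment for Aim 9, and the column does not describe the structured protocol that the SAP mentions. Its silence therefore shows that no comparator is documented. It does not show that only one condition was run.

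**The illustrations are limited.** An increase has a natural default of above zero, so the missing threshold is a lesser gap than the missing time points. Set 2 has a negative mean because of four large losses; its median is +0.3 and its t-test would give p = 0.30. It shows a responder count and a mean differing in sign. It does not show the plan's selected test contradicting the count.

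**Conclusion.** The concern holds and must be fixed. As worded, the Aim 9 primary outcome is one yes/no status per participant, and the prescribed paired tests cannot be run on it. If the continuous volume change was intended, the tests can stand, and the defect reduces to the outcome wording and the unnamed pair. Either way the primary analysis is not determined by the plan.

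No inflation of error rates is claimed. Confidence is high for the mismatch between outcome and test, which rests on the text alone. The numerical illustrations rest on assumed n, an assumed normal distribution and invented values, and they say nothing about the trial's actual results.

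**What to change.** Amend the Aim 9 section to state one of two options.

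- **(a) Continuous outcome.** Restate the primary outcome as each participant's percent change in limb fluid volume. Name the two paired time points or conditions. Keep the paired t-test or signed-rank test.
- **(b) Responder outcome.** Define an increase by threshold and time points. Report k/n with a Clopper-Pearson 95% CI. Remove Shapiro-Wilk, the paired t-test and the signed-rank test for this variable. No hypothesis test is required. Use exact McNemar only if two conditions are named, and an exact binomial test only if a reference rate is stated and justified.

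Under both options, report how many participants had no bioimpedance data, because electrode placement is optional in the procedures table. Label as post hoc any scale, threshold, time point or reference rate set after Aim 9 data were seen; the section already describes the assessment in the past tense.

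The cost is a few sentences, with no new visits or data. Option (b) makes the aim descriptive unless a pair or reference rate is justified, and the interval will be wide: about 46 to 76 percentage points at 50% responders for an assumed n of 20 down to 6.

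### Aim 9's primary outcome counts participants whose limb fluid volume rose but sets no minimum change, so the proportion reported alone cannot be read as a response to the socket

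*Combined protocol and SAP*

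**What the plan says.** The SAP section for Aim 9 opens by giving its primary outcome measure as "participants who experienced increase in limb fluid volume was assessed after a structured protocol involving socket enlargements and socket reductions". This is a yes/no status for each participant. The section gives no minimum change, upper limit, baseline time, error allowance or target proportion. It then applies tests meant for a continuous paired measure ("Normally distributed data will be compared using paired t-tests", otherwise a Wilcoxon signed rank test) and closes: "A significance level of 0.05 will be used to determine whether differences were statistically significant between interventions". It does not name the interventions compared in Aim 9.

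The text after the visit tables names the instrument, "a bioimpedance measurement system to assess limb volume changes", but gives no repeatability. For Aims 2, 6A, 6B and 8, the SAP takes the change in limb volume itself as the primary outcome.

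On purpose, the Study Protocol section says of the system: "It helps to maintain consistent limb fluid volume when the service member or Veteran is actively using the prosthesis". It also names two design concepts, of which the second reads: "The other concept is to loosen the socket during resting to allow healthy fluid return to the limb". Under Specific Aims, Aim 9 concerns a liner-attached socket "that is able to quickly enlarge and quickly return to normal size automatically during ambulation".

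**The concern.** Without a minimum change, a participant whose volume did not really move is classified by the sign of the measurement error. A trivial rise and a large one count the same, and a volume held exactly steady is not counted at all. A sizeable share of increasers could then be presented as a favourable finding although the socket had no effect. The count also cannot separate steady volume from upward drift, and both matter for a system described as keeping volume consistent. Changing the statistical test would not repair this, because the fault lies in what is counted.

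**Working it through.** The documents give no sample size, effect size, error SD or expected proportion for Aim 9, so there is no figure of the plan's to reproduce.

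**Inputs**
- Threshold c = 0: the literal reading of the SAP, Aim 9.
- True mean change d, in SDs of the measured change: not given; assumed range −1 to +1, with +2 and +3 for large rises.
- Error: assumed normal. Symmetry alone is enough for the 50% figure.
- Number of participants n: not given; 10, 12 and 20 assumed.
- Significance level: 0.05 (SAP, Aim 9; sidedness not stated).

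**1. Share counted with no threshold.** P(counted) = 1 − Φ(c − d), which is Φ(d) when c = 0.

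| d (SD) | −1 | −0.5 | −0.25 | 0 | +0.25 | +0.5 | +1 |
|---|---|---|---|---|---|---|---|
| counted | 15.9% | 30.9% | 40.1% | 50.0% | 59.9% | 69.1% | 84.1% |

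The 50% belongs to exactly zero drift. A modest shared drift, whatever its cause, moves it a long way.

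**2. No upper end.** At d = +2 and +3 the share is 97.7% and 99.9%. A large rise therefore scores better than a constant volume.

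**3. What chance alone produces.** With p = 0.5, the binomial probability that at least 70% of participants are increasers is 17.2% for n = 10 (7 or more: 176/1024), 7.3% for n = 12 and 5.8% for n = 20. These are not false-positive rates at 0.05. A one-sided exact test against 50% with n = 10 needs 9 of 10 (11/1024 = 0.011), since 8 of 10 gives 56/1024 = 0.055.

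**4. With an error-based threshold.** Take c = 1.96, in SDs of the error of a change score. This is the same unit as in step 1 if participants do not differ in true change. At d = 0, 2.5% are called gained and, by symmetry, 2.5% lost, leaving 95.0% with no detectable change. The remainder is 83.0% at d = 1, 48.4% at d = 2 and 14.9% at d = 3.

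**5. Effect on a comparison of two conditions.** If neither condition changes volume, both give 50% and the expected difference is zero, so noise creates no false effect. If one has d = +1 and the other d = 0, the sign count differs by 84.1 − 50.0 = 34.1 percentage points. The thresholded count differs by 16.9 − 2.5 = 14.4 points. A threshold makes the individual label credible but does not sharpen a group contrast, which is a reason to analyse the continuous change and keep any count descriptive.

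**The case against.** The strongest reply is that the text sets no rule of this kind. It does not speak of success and does not say that any increase suffices; both are inferences from silence. That is right, and the point is limited accordingly: the criterion is undefined, and its literal reading has the properties shown. For a primary outcome the definition has to be in the plan.

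A reader might infer that the outcome contradicts the device's purpose, because volume should be kept consistent. The documents do not support that. The second design concept makes fluid return a benefit, so an increase can be a legitimate target. The fit is not complete, since that concept is tied to rest and Aim 9 to ambulation, but this calls for stating the target and does not show that the endpoint is wrong.

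A reader might also infer that half of all participants would be false responders, or that the trial has an inflated false-positive rate. Neither follows. The 50% needs zero drift, and a paired comparison would mainly be diluted. The SAP does refer to differences between interventions. It names no comparator for Aim 9, however, so a proportion reported alone cannot be excluded.

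Finally, it is tempting to make a steady volume the success category. That would be worse: with a band of ±1.96 SD, about 95% would succeed with an inert socket, and a noisier instrument would widen the band.

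**Conclusion.** The concern holds in limited form. The Aim 9 primary outcome has no minimum change and no error allowance, and nothing elsewhere in the documents supplies them. Read literally, about half of participants are counted when the true change is zero and error is symmetric. Under a normal model the share is 16% to 84% for assumed drifts of −1 to +1 SD of the measured change. The proportion on its own therefore cannot be read as a response to the socket. The drift, the error distribution and the numbers of participants are assumptions, because the documents give none of them. The point does not establish an inflated error rate or a wrongly chosen endpoint.

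**What to change.** 1. Make each participant's continuous change in limb fluid volume the analysed quantity for Aim 9, as for Aims 2, 6A, 6B and 8, and use the paired t-test or Wilcoxon test already named. State the baseline, the measurement time and the conditions compared.
2. If a count is kept, call a participant *gained* or *lost* only when the change exceeds 1.96 SD of the error of a change score, estimated from repeat bioimpedance readings in the same session. Show the remainder as *no detectable change*, not as success, and list each participant's change.
3. State whether gain or stability is the Aim 9 target.

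The cost is mostly SAP wording. The reported share with an increase will be lower. Step 2 assumes usable repeat readings. The visit table for Aim 9 describes standing, then treadmill walking at varying speeds, and makes electrode placement optional, so their availability must be confirmed. The SAP describes the outcome in the past tense. If the data have already been seen, the change should be dated and labelled as made afterwards, with the count reported beside it.
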